Biostatistician
Division of Biostatistics
Clinical Research Office, Loyola University Chicago
[name]
[name]
Email: [contact]

Research Office: Clinical Research Office (CRO)
Stritch School of Medicine, Loyola University Chicago
[name]
[name]
[name]
[contact]
[contact]

LU 210546

Version 10/23/17

Signature Page

The signature below constitutes the approval of this protocol and the attachments, and provides the necessary assurances that this trial will be conducted according to all stipulations of the protocol, including all statements regarding confidentiality, and according to local legal and regulatory requirements and applicable U.S. federal regulations and ICH guidelines.

Principal Investigator (PI) Name: _____

PI Signature: _____

Date: _____

[figure not shown]
STUDY SUMMARY	
Title	BEACON - A phase I/II study of high-dose-rate Brachytherapy and External beam and short-term Androgen deprivation CO mbined for the treatment of Men with Fluciclovine PET Pelvic Nodal Uptake in locally recurrent prostate cancer after prior definitive radiotherapy
Short Title	Combined salvage high dose rate brachytherapy, external beam and short-term hormonal therapy for local recurrent prostate cancer with fluciclovine PET uptake in pelvic nodes after radiotherapy
Protocol Number	***
Methodology	Phase I/II Non-randomized trial
Study Duration	5 years
Study Center(s)	Loyola University medical Center, Stritch School of Medicine, Loyola University Chicago
Objectives	
 1. To determine the 3 month grade ≥ 3 radiation-related genitourinary and gastrointestinal toxicity of this treatment approach (primary endpoint) 2. To describe the acute and late toxicity profile with this approach 3. To evaluate disease control efficacy outcomes (biochemical progression-free survival, local control, regional recurrence, cause-specific survival, overall survival, etc.) 4. To evaluate patient reported health related quality of life following this treatment approach 5. To describe the dosimetry in patients undergoing this approach
Number of Subjects	24

LU 210546

Version 10/23/17

Diagnosis and Main Inclusion Criteria	
 • Biopsy-proven local recurrence of prostate adenocarcinoma (biopsy within 182 days) • Pathologic Fluciclovine uptake in pelvic lymph nodes without distant metastases • Current AUA International Prostate Symptom Score (IPSS) score <20 • Initial disease stage cT1-3a NX or N0 • Treated with prior definitive radiation therapy using any radiotherapeutic modality (prior whole pelvis RT ineligible)
Duration of Administration	2 brachytherapy implants, ~5-8 weeks of daily radiation, 6 months hormonal therapy
Statistical Methodology	
This study is designed as a two stage Phase I/II, non-randomized study. In the first stage, 7 patients will be accrued. If there are 2 or more toxic responses in these 7 patients, the study will be stopped for safety reasons. Otherwise, 17 additional patients will be accrued for a total of 24 patients.
 
Assuming that the true toxicity rate in the population is 10% or less, the study is powered to reject the null hypothesis that the toxicity rate is 33% or higher. A toxicity event is defined as an acute grade ≥ 3 radiation-related toxicity as assessed by the Common Toxicity Criteria for Adverse Events version 4.
 
Standard non-parametric or parametric methods will be used to describe these patients' demographic and clinical information as well as their dosimetric information. The primary aim of the study is to estimate the toxicity rate of HDR brachytherapy among patients with recurrent prostate cancer. A one-tailed test for a difference in proportions will be used to determine whether the observed toxicity rate is lower than the hypothesized toxicity rate. The null hypothesis that the toxicity rate is 33% or higher will be rejected if more than 19 (non-toxic) responses are observed in 24 patients. When the true toxicity rate is 10.0%, this design yields a type I error rate of .046 and power of 81%.
 
We also will describe the freedom from biochemical recurrence, relapse-free survival, local control, elsewhere-prostate control, freedom-from local failure, freedom from distant metastasis, freedom from hormonal therapy, disease-free survival, cause-specific survival, and overall survival.

Study Schema

LU 210546

Version 10/23/17

Table of Contents

Title page.....	i
Signature page.....	iv
Study Summary.....	v-vi
Study Schema	vii
List of Abbreviations	x
1.0 Background and Rationale	1
1.1 Disease Background and Lessons from Other Malignancies	1

CSS	cause specific survival
CTCAE v4.03	Common Toxicity Criteria for Adverse Events, version 4.03
CTV	clinical target volume
DM	distant metastasis
DFS	disease-free survival
DRE	digital rectal exam
DSMP	Data Safety Monitoring Plan
EBRT	external beam radiotherapy
EPC	elsewhere prostate control
EPF	elsewhere prostate failure
FDA	Food and Drug Administration
FFBR	freedom from biochemical recurrence
FFDM	freedom from distant metastasis
FFEPF	freedom from elsewhere prostate failure
FFHT	freedom from hormone therapy
FFLF	freedom from local failure
FFRF	freedom from regional failure
GCP	good clinical practice
GI	gastrointestinal
GS	Gleason score
GTV	gross tumor volume
GU	genitourinary
HDR	high-dose rate
HiFU	high intensity focused ultrasound
I-125	Iodine-125
IPSS	International Prostate Symptom Score
Ir-192	Iridium-192
IRB	Institutional Review Board
LC	local control
LDR	low-dose rate
LF	local failure
LRPC	locally recurrent prostate cancer
MP-MRI	multi-parametric MRI
OS	overall survival
PCA	patient controlled analgesia
Pd-103	Palladium-103
LU 210546	

PSA	prostate specific antigen
PTV	planning treatment volume
RC	regional control
RF	regional failure
SAE	serious adverse event
UPR	unanticipated problems

LU 210546

Version 10/23/17

1.0 BACKGROUND AND RATIONALE

1.1 *Disease Background and Lessons From Other Malignancies*

Prostate cancer is the most common cancer diagnosed in men and ranks second in cancer-related deaths among all men in the United States in 2012. In 2014, 177,489 men were diagnosed with prostate cancer, with 27,244 annual deaths.¹ Radiotherapy is a curative treatment option for these patients, yet a significant proportion of patients, particularly those with more aggressive disease, will go on to develop biochemical recurrence after curative treatment, and thereafter typically develop nodal and/or distant metastases from their progressed malignancy. For the patients who specifically present with nodal recurrence after curative radiotherapy, palliative androgen deprivation therapy (ADT) has been the primary treatment. However, ADT is not curative, and patients typically progress to castrate resistant disease over time and ultimately develop clinical progression of disease. In patients with a long life expectancy, identifying a way to salvage the patients who have local and regional disease alone could result in more durable disease outcomes and potential prevent morbidity and mortality.

In many disease sites, patients who had regional recurrence of disease are treated with aggressive salvage therapy in order to try for cure of the malignancy. An example of this includes patients who have mediastinal recurrence after SBRT or lobectomy for lung cancer. These patients are typically treated with definitive doses of concurrent chemoradiotherapy or sometimes with repeat SBRT in the setting of a local recurrence.²⁻⁴ In head and neck cancer, patients are typically treated with regional chemoradiotherapy if they have had treatment of the primary but develop recurrence in the cervical lymph nodes. Additionally, reirradiation is an established treatment approach for patients with recurrence of disease.

Thus, an important question is whether the principles of all of these other malignancies can be applied to prostate cancer, as radiation has the potential to deliver curative treatment to regional disease in the definitive setting and brachytherapy can deliver curative treatment for local disease.⁵⁻⁷

Evidence for Salvage Local Therapy to the Prostate in Prostate Cancer

Even after initial treatment of prostate cancer with definitive radiation, biologic PSA failure can occur in up to 50% of patients.^{8,9} However, in the patients who develop biochemical progression, up to 55% of those patients will have local recurrence alone, with the majority of those recurrences at the site of the dominant primary tumor.¹⁰ For these men with local recurrence alone, treatment options include both palliative and definitive approaches. Often times, in this setting, men are treated with a palliative approach of continued PSA surveillance without intervention or androgen deprivation therapy (ADT). However, neither of these modalities is curative. Furthermore, the use of ADT is associated with side effects

of up to 80% of patients, including hot flashes, fatigue, gynecomastia and sexual dysfunction, leading to a 16.4% treatment cessation.^{11,12}

Standard curative treatment options in the salvage setting after radiotherapy include salvage prostatectomy, cryosurgery, or brachytherapy to the prostate¹³

The decision of which salvage treatment modality to utilize is difficult, as there are no randomized data supporting one modality over another. Parekh, et al reported a systemic review comparing the oncologic benefits and toxicity profiles of radical prostatectomy, brachytherapy, cryotherapy, and high-intensity frequency ultrasound (HiFU) in the salvage setting after definitive external radiation. They found a similar rate of failure-free survival at 5 years across all salvage modalities, ranging from 52-56%. Salvage brachytherapy had a failure-free survival of 55.6%. Regarding toxicities, compared to the other modalities, brachytherapy had the lowest rate of incontinence (6.16%) and the second lowest rate of bladder neck stricture (7.48%). The rate of fistula formation was greatest in the Hifu group, followed by brachytherapy, although this rate was still quite low at 3.09%. Prostatectomy carried the highest rates of incontinence (49.7%) and stricture (26.09%).¹⁴

1.2 *Salvage brachytherapy*

An additional treatment option in the setting of locally recurrent prostate cancer (LRPC) after definitive EBRT that has gained recent attention is the use of interstitial brachytherapy.¹³ Brachytherapy is beneficial in the salvage setting due to its inherent ability to deliver a higher dose to a smaller area, thus sparing the previously irradiated surrounding normal tissues, and decreasing toxicity. This includes both low-dose-rate (LDR) and high-dose-rate (HDR) brachytherapy techniques, which have been studied in a variety of phase I/II trials and retrospective series, with the majority of available data reporting on LDR brachytherapy technique. Overall, the limited data on salvage brachytherapy show promising results, with both the achievement of biochemical disease control and the with treatment related toxicities, which are either comparable to or better than alternative salvage options.

There are limited retrospective data on the use of salvage LDR brachytherapy. Grado, et. al. describes a cohort of 46 men treated with LDR brachytherapy for LRPC after definitive EBRT, utilizing I-125 or Pd-103 radioactive seeds treating to 130-140Gy median matched peripheral dose. He reports a 5 year cause specific survival of 79%, a local control rate of 97% at latest follow-up with a low, 6% rate of severe urinary or rectal toxicities.¹⁵ Another group, Beyer, et. al reported on a cohort of 17 men treated with LDR brachytherapy after definitive EBRT using I-125 or Pd-103, treated with a median peripheral dose of 97-100Gy. Their reported 5 year OS was 93% and freedom from biochemical relapse was 53%.¹⁶ There is a current ongoing RTOG/NRG trial evaluating the use of salvage LDR brachytherapy in men treated with prior EBRT with initially diagnosed T1-T2c,

GS 2-7, PSA<20ng/mL, utilizing I-125 radioactive seeds treating to 140Gy minimum target dose or Pd-102 treating to minimum target dose of 120Gy.¹⁷

There is evidence supporting salvage HDR for patients with locally recurrent prostate cancer, primarily delivered to the whole prostate gland due to uncertainty about the geographic location of the local recurrence with older imaging techniques. Yamada, et al reported their results of a phase II study of 42 patients treating LRPC with salvage HDR brachytherapy after prior definitive external radiation. Their prescribed dose was 32Gy delivered in four fractions over 30 hours using a single implant. At a median follow-up up 26 months, they reported an actuarial 5-year biochemical recurrence free survival of 68.9% and a distant metastasis free survival of 81.5%. Regarding toxicities, acute genitourinary (GU) grade 1 and 2 toxicities rates were 38% and 40%, respectively, and 38% and 48% had late grade 1 or 2 GU toxicities. Only 1 of 42 patients developed late grade 3 toxicity of urinary incontinence, and 3 patients (7%) developed a late grade 3 urinary stricture corrected with urethral dilatation. Late grade 1-2 gastrointestinal (GI) toxicities occurred in 43% and 14% of patients, but there were no late grade 3+ GI toxicities.¹⁸ Chen, et al reported a retrospective study of 52 patients receiving 36 Gy in six fractions given in two separate implants, 1 week apart. 5-year biochemical control was 51%, with a 2% incidence of grade 3 or higher late GU toxicity and no late grade 3+ GI toxicity.¹⁹

1.4 *Rationale for Salvage Regional Therapy to the Pelvic Lymph Nodes in Prostate Cancer*

There are emerging data that some patients who have recurrent disease in the pelvis may benefit from aggressive regional cancer-directed treatment with surgery or radiotherapy. Prospective studies have examined post-prostatectomy patients presenting with biochemical recurrence who underwent salvage pelvic lymph node dissection (PLND) of their [11C] choline PET/CT positive nodal disease. In a study by Rigatti et al 83.3% of patients with positive nodal metastases on [11C] choline PET/CT, had pathologic positive prostate cancer.²⁰ Following salvage lymph node dissection, a total of 41 patients (56.9%) had a subsequent biochemical response (defined as PSA <0.2). Ultimately, they found a 5-yr biochemical-free survival rate of 19% and concluded that salvage lymph node dissection in patients with nodal uptake on [11C] choline PET/CT can lead to a delay of clinical progression and a complete biochemical response can be achieved in a small proportion.

Another study by Suardi et al looked at the 5-yr results of patients following salvage PLND. They found that in their cohort of patients with a mean number of 29.5 nodes removed at the time of surgery, 47 patients (79.6%) had positive lymph nodes. Overall, 35 patients (59.3%) experienced biochemical response following surgery and this led to a 22.1% 8-yr biochemical-recurrence free survival. Therefore based on these results they concluded in patients with a small

volume of nodal recurrence a meaningful biochemical complete response after salvage LND can be achieved.²¹

With increasing use of imaging such as (18) F-fluciclovine PET/CT we are better able to detect occult nodal disease, even in those with low PSA levels.²² Given that surgical series have shown improved biochemical response in patients with positive pelvic nodes detected on functional imaging, radiotherapy has a distinct advantage in that it can target gross disease as well as microscopic disease, and is non-invasive and an option for most patients.

The primary limitation to adding on radiotherapy to the pelvic nodes is the risks of reirradiation in areas of overlap. However, using modern sophisticated treatment planning methods such as intensity-modulated radiotherapy (IMRT) and volumetric arc therapy (VMAT), areas of overlap in critical structures can be minimized while delivering curative doses to target lesions.

1.5 *Rationale for current study*

Salvage regional and local radiation is frequently utilized across multiple disease sites in oncology for patients who have failed initial radiotherapy. However, in prostate cancer, due to the concern that nodal involvement is a manifestation of widespread distant disease, this type of approach has not typically been pursued. However, with newer imaging modalities such as fluciclovine PET, PSMA pet, and C11 PET, we are identifying nodal disease and excluding distant disease better than we ever have before. Thus, in this modern era regional control may translate to improved long-term biochemical control, and prevent the morbidity and mortality associated with clinical progression of biochemically recurrent prostate cancer

Thus, in patients who recur both in the prostate and in the pelvic lymph nodes, treating both with radiation could result in meaningful clinical efficacy for patients—similar to other disease sites. However, there are limited data exploring the feasibility and safety of this combination. Therefore, we propose this trial, combining salvage HDR brachytherapy to locally recurrent prostate cancer in the prostate and EBRT to the pelvis, both in the setting of short-term hormonal therapy, in patients who have developed local recurrence with regional pelvic nodal PET uptake after definitive radiation. We hypothesize that this approach can safely be performed without excess toxicity. Ultimately, we hope to use data from this Phase I/II study to create a multi-institutional phase III study in which we could analyze whether this treatment approach can improve disease control and survival outcomes when compared to standard palliative hormonal therapy.

2.0 STUDY OBJECTIVES

2.1 *Primary Objective*

2.1.1 To determine the incidence of acute grade ≥ 3 radiation-related genitourinary (GU) and gastrointestinal (GI) toxicity of this treatment approach

2.2 *Secondary Objectives*

- 2.2.1 To describe the acute and late toxicity profile with this approach
- 2.2.2 To evaluate disease control efficacy outcomes (biochemical progression-free survival, local control, regional recurrence, cause-specific survival, overall survival, *etc.*)
- 2.2.3 To evaluate patient reported health related quality of life following this treatment approach
- 2.2.4 To describe the dosimetry in patients undergoing this approach

2.3 *Endpoints*

2.3.1 Primary Endpoint:

2.3.1.1 3-month radiation-related grade ≥ 3 GU and GI toxicity as defined by Common Terminology Criteria for Adverse Events (CTCAE) v4.03 (Link available in Appendix A).

2.3.2 Secondary Endpoints:

2.3.2.1 All-grade acute and late toxicity as defined by CTCAE v4.03 criteria (see Appendix A)

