3.1.6 Current ECOG Performance status Scale 0-2 (Appendix D)

3.1.7 Current International Prostate Symptom Score (IPSS) < 20 (Appendix B)

3.1.8 Age ≥ 18

3.1.9 The patient must be medically suitable to receive general or spinal anesthesia.

3.1.10 AST, ALT, and alkaline phosphatase < 2 x upper institutional limit within 3 months of registration.

3.1.11 The patient must be able and willing to sign a study-specific written informed consent form before study entry.

3.2 *Exclusion Criteria*

- 3.2.1 Preregistration GI or GU toxicity (for any reason) grade ≥ 3 as defined in CTCAE version 4.03. That is, grade ≥ 3 GU or GI toxicity after first course of radiotherapy
- 3.2.2 Treatment to a “whole pelvis” field with initial radiotherapy
- 3.2.3 Prior radiotherapy to the region of the body that is intended to be the target with the current course of RT.
- 3.2.4 Patients with distant metastases (such as to the bone, visceral organs, and lymph nodes other than the pelvic nodes including the common iliac nodes).
- 3.2.5 Patients receiving any other investigational agents.
- 3.2.6 Uncontrolled inter-current illness including, but not limited to, ongoing or active infection, severely symptomatic congestive heart failure, cardiac arrhythmia, recent myocardial infarction in last 6 months, or psychiatric illness/social situations that could limit compliance with study requirements.
- 3.2.7 Patients who have received chemotherapy or immunotherapy within one month prior to study enrollment, other than ADT.

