8.1.8 Adverse event assessment

Baseline adverse events from prior radiotherapy regimen will be assessed. See section 10.0 for adverse event monitoring and reporting.

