8.1.11 Labs

AST, ALT, Alkaline Phosphatase, and any labs required for the brachytherapy procedure as part of usual care.

8.2 *Follow-up Procedures*

Patients will be followed as described in Section 8.3.

8.3 *Study Parameters*

	Pre-study	Start of EBRT	Week 4 post-treatment	Month 3 & 6	Month 12	Follow-up Q 6 months*	Time of Biochemical Recurrence
Informed Consent	X						
History and PE, including DRE	X		X	X	X	X	
Medication Assessment	X		X	X	X	X	
Performance Status	X		X	X	X	X	
Toxicity Assessment			X	X	X	X	
PSA	X			X	X	X	
Bone scan	X						X
MP-MRI	X						X¥
PET/CT	X						
IPSS score	X		X	X	X	X	
EPIC-26	X		X	X	X	X	
AST/ALT/ALK PHOS	X	X					

* Until disease progression, death, or follow up period is complete

¥If MP-MRI reveals any suspicious lesions, then biopsy is encouraged.

DRE – Digital Rectal Exam

PE – Physical Exam

MP – Multi-parametric

EBRT – External Beam Radiotherapy

8.4 *Removal of Subjects from Study*

Patients can be taken off the study treatment and/or study at any time at their own request, or they may be withdrawn at the discretion of the investigator for safety, behavioral, or administrative reasons. The reason(s) for discontinuation will be documented and may include:

- 8.4.1 Patient voluntarily withdraws prior to treatment;
- 8.4.2 Patient withdraws consent (termination of treatment and follow-up);
- 8.4.3 Patient is unable to comply with protocol requirements;
- 8.4.4 Patient develops interval co-morbidity that makes continuation in the protocol unsafe;
- 8.4.5 Treating physician(s) judge(s) the study would not be in the patient's best interest;
- 8.4.6 Development of second malignancy (except for basal cell carcinoma or squamous cell carcinoma of the skin) that requires treatment, which would interfere with this study;
- 8.4.7 If a research subject cannot be located to document survival after a period of 2 years; the subject may be considered "lost to follow-up". All attempts to contact the subject during the two years must be documented and approved by the Data Monitoring Committee.

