12.3 Data Analyses Plans

For this single group trial, summary frequencies and statistics will be provided for all relevant patient characteristics and clinical measures, including demographics (e.g., age, cancer stage, educational attainment, etc) as well as clinical outcomes (e.g., laboratory monitoring, adverse event monitoring, etc.). These include valid counts with percentages for categorical and ordinal variables as well as median with interquartile range or mean with standard deviation or standard error for continuous variables.

For the primary aim, a one-tailed one-sample test for proportions will be used to test whether the observed toxicity rate is lower than the hypothesized toxicity rate. For relapse-free survival, death will *not* be considered a competing event.

Instead, a two-sided one-sample log-rank test will be used to estimate the probability of being relapse free 24 months following treatment.

The instantaneous risk of relapse or death may be estimated as a function of age, cancer stage, and other covariates using semi-nonparametric Cox proportional hazards models. For these models, the number of covariates used for the adjustment will be determined by the number of events. Approximately one predictor for every 10 relapse or mortality events may be used to determine adjusted survival probabilities as described by Peduzzi et al.²⁴ For all Cox proportional hazards models, the proportional hazards assumption will be evaluated using Martingale residuals as described by Lin, Wei, and Ying.²⁵ If the proportional hazards assumption is violated, parametric accelerated failure time models may be used assuming the true underlying hazard distribution is identified.

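### The all-grade toxicity endpoint has no baseline reference, so unchanged grade 1-2 GU/GI toxicity left by earlier radiotherapy could be tabulated as toxicity of the salvage approach

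*Combined protocol and SAP*

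**What the plan says.** **Objective and endpoint.** Secondary objective 2.2.1 is "To describe the acute and late toxicity profile with this approach". The matching endpoint, 2.3.2.1, is "All-grade acute and late toxicity as defined by CTCAE v4.03 criteria". The primary endpoint in 2.3.1.1 is limited to radiation-related events. Endpoint 2.3.2.1 carries no such limit and no condition that an event be new or worse than at entry.

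**Who can enter.** All men have had definitive radiotherapy to the prostate (3.1.1, 3.1.3). Exclusion 3.2.1 removes men with "Preregistration GI or GU toxicity (for any reason) grade ≥ 3 as defined in CTCAE version 4.03", so grades 1 and 2 remain eligible. Criterion 3.1.7 requires "Current International Prostate Symptom Score (IPSS) < 20 (Appendix B"), so a score of up to 19 is allowed; Appendix B labels 8-19 as moderate.

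**Baseline.** Section 8.1.8 states: "Baseline adverse events from prior radiotherapy regimen will be assessed". It then refers to section 10.0 for monitoring and reporting. In the section 8.3 table, the row "Toxicity Assessment" has no mark at Pre-study or at Start of EBRT; its first mark is at Week 4 post-treatment.

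**Analysis.** Section 12.3 covers clinical outcomes, with adverse event monitoring among its examples. Of the summaries it says: "These include valid counts with percentages for categorical and ordinal variables". It mentions no change from baseline, treatment-emergent definition or shift table.

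**The concern.** In a single-arm re-irradiation trial, each man's own state at entry is the only internal reference for what the salvage course did to him. The protocol recognises carry-over from the earlier course, since it asks for it to be assessed at screening, but no analysis uses that information.

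Take two men who both have grade 2 urinary frequency at Month 3. One had it at entry and is unchanged; the other entered at grade 0. A plain count of grades does not tell them apart. If the all-grade table is built that way, it mixes residual harm from the earlier course with harm from the salvage course, and grade 1-2 rates are too high as a description of the salvage approach.

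Section 1.5 says the data are meant to support a phase III comparison with palliative hormonal therapy, so the low-grade toxicity profile will be read and reused.

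**Working it through.** **1. The plan's own figures, to see whether they are touched.** The design in 12.2 continues if at most 1 of 7 men has a toxic response, and rejects the null hypothesis if at most 4 of 24 do (more than 19 non-toxic).

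- Early stopping at a 33% rate: 1 − [0.67^7 + 7 × 0.33 × 0.67^6] = 0.730 (stated 73%).
- Type I error: the exact two-stage binomial probability of at most 1 of 7 and at most 4 of 24. At 33% this is 0.0462 (stated .046).
- Power: the same probability at 10% is 0.809 (stated 81%).

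All three reproduce. They concern acute grade 3 or higher GU/GI events. Since 3.2.1 removes men with such toxicity before registration, any grade 3 or higher GU/GI event after treatment is already worse than baseline. The concern does not reach the primary test or the stopping rule.

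**2. Do other provisions supply the missing baseline rule?**

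| Provision | What it does | Does it close the gap? |
|---|---|---|
| 10.3.1, adverse event definition | Any untoward occurrence in a man on study treatment | Does not explicitly require onset or worsening after entry |
| 10.3.1, relatedness review | Radiation-related or not, judged by treating physician and principal investigator | Does not explicitly separate the earlier course from the salvage course; not tied to 2.3.2.1 |
| 10.4, attribution categories | Grade relation to the radiation treatment | Same limits; written for expedited reporting |
| 10.2, return to baseline | Ends monitoring of an event | Not an analysis rule |
| 8.1.10 and 8.3, IPSS and EPIC-26 | Patient-reported scores at baseline and follow-up | Show change in symptoms, but do not correct CTCAE grades |

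**3. Possible size.** The documents give no baseline prevalence and no expected grade 1-2 rate, so every input here except N = 24 is an assumption. Let b be the proportion of men whose baseline grade 1-2 toxicity persists into follow-up, and i the true proportion with new or worsened toxicity, taken as independent of b.

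- Apparent rate = b + (1 − b) × i
- Inflation = b × (1 − i)

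With i = 30%, the true count is 24 × 0.30 = 7.2 men.

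| Assumed b | Apparent rate | Men of 24 | Inflation (points) |
|---|---|---|---|
| 5% (10% prevalence, half persisting) | 0.05 + 0.95 × 0.30 = 33.5% | 8.0 | 3.5 |
| 20% | 0.20 + 0.80 × 0.30 = 44% | 10.6 | 14 |
| 50% | 0.50 + 0.50 × 0.30 = 65% | 15.6 | 35 |

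The inflation is upward wherever b is above zero and i is below 100%. Its size depends almost entirely on b, which the documents do not give.

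**The case against.** The strongest reply is that the plan is silent, not wrong. The sentence in 12.3 sets a format for all categorical and ordinal variables, and counts with percentages would suit treatment-emergent counts or a shift table equally well. Section 8.1.8 already labels these events as belonging to the prior regimen. Section 10.2 treats return to baseline as the end of an event, which fits poorly with calling an unchanged baseline symptom an adverse event. This stands in part: a reader might infer that the plan directs pre-existing toxicity to be counted as toxicity of the salvage regimen, and no passage says so. The text supports only that it could be, because no rule prevents it.

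A reader might also infer that true worsening would be invisible. That is not supported. IPSS and EPIC-26 are taken at baseline, Week 4, Months 3, 6 and 12, and every 6 months thereafter. They are a named secondary endpoint (2.3.2.11) and cover urinary and bowel symptoms. CTCAE worsening could also be derived wherever baseline grades were recorded.

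Two further points stand. An IPSS of up to 19 is a symptom score, so it does not show that entrants have radiation toxicity. And objective 2.2.1 is descriptive, with no test or threshold attached; overstating harm is the cautious direction in a safety study. That limits the consequences, but a profile inflated by an earlier treatment still does not answer the stated objective.

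**Conclusion.** The point holds as a gap in the analysis plan for a descriptive secondary endpoint. Men with grade 1-2 GU/GI toxicity can enter, the endpoint is all-grade with no baseline qualifier, and neither 12.3 nor section 10 says how pre-existing toxicity is handled in the summary. Grade 1-2 rates could be biased upward. The primary endpoint, N = 24, the type I error of .046 and the power of 81% do not change.

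The size cannot be established from the documents. The 44-65% against 30% illustration shows what is possible under assumed prevalence, full persistence and independence; it is not an estimate. Low prevalence with partial persistence would add only a few points.

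Nor can it be taken for granted that the baseline data will exist. Section 8.1.8 calls for the assessment, but the 8.3 schedule does not mark it, and 8.1.8 does not itself say that a CTCAE grade is to be recorded. Without baseline grades, the CTCAE table could not be adjusted later.

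**What to change.** - **Section 12.3:** report the worst acute and worst late GU and GI grade as new or worsened relative to each man's baseline CTCAE grade. For each period, add a table of baseline grade by worst post-treatment grade. Keep the raw grade table beside it so that nothing is hidden.
- **Endpoint 2.3.2.1:** refer to that rule.
- **Sections 8.1.8 and 8.3:** reconcile them by marking a toxicity assessment at Pre-study in the schedule, and state that the CTCAE v4.03 grade is recorded.

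The cost is one extra table and recording the baseline grade at screening. Section 8.1.8 already requires the assessment, and exclusion 3.2.1 already requires prior GI/GU toxicity to be judged against CTCAE. No visit is added and no treatment rule changes.

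One limit remains: late effects of the earlier course that first appear after salvage would still count as new. Baseline referencing removes only what was present at entry, and the report should say so.
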